Specifically, the mouth-end of the cannabis pipe and the tobacco product (either tobacco cigarettes or the JUUL) is inserted into a specialized mouthpiece (custom-made to firmly fit either product) and users inhale the product through the mouthpiece; a sensor inside the mouthpiece detects puff-induced pressure changes which are then used to derive data for the various topography variables (e.g., puff duration, puff volume). This topography-recording equipment has been used in several other clinical laboratory examinations of cannabis, conventional cigarettes, and e-cigarettes (McClure et al., 2012; Ramoa et al., 2016; Spindle et al., 2018) and has been demonstrated to not interfere with acute e-cigarette effects when compared to e-cigarette use without the equipment present (Spindle et al., 2017).

Vital signs (heart rate, systolic blood pressure (SBP), diastolic blood pressure (DBP)) will be measured in the seated position before (i.e., baseline), and approximately 5, 30, 60, 90, 120, 180, 240-and 360-min after cannabis exposure.

The Drug Effect Questionnaire (DEQ) (Spindle, 2018; Vandrey et al., 2017) will be used to obtain subjective ratings of drug effects. Individual items include ratings of general positive/negative drug effects (e.g. drug effect, good effect, bad effect, liking) and behavioral/mood states often associated with cannabis intoxication (e.g. relaxed, paranoid, hungry/have munchies). The DEQ will be administered before (i.e., baseline), and approximately 5, 30, 60, 90, 120, 180, 240-and 360-min after cannabis exposure. We expect that all subjective drug effects will subside within 5 hours (360 min) of cannabis exposure based on recent and ongoing studies in our laboratory.

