Primary outcome variable is the amount of nicotine used (determined by total volume of cigarette smoke or JUUL vapor inhaled) after cannabis exposure in each session. We hypothesize that exposure to active cannabis will result in greater nicotine use compared with placebo cannabis.

b. Secondary outcome variables.

Secondary outcome variables include other nicotine use behaviors (amount self-administered and puff topography outcomes), subjective drug effect ratings, cognitive and psychomotor performance, and vital signs (HR, BP). We hypothesize that nicotine use will increase subjective drug effect ratings and decrease cognitive performance after exposure to active cannabis compared with the experimental session in which no nicotine/tobacco products are consumed. We also expect that active cannabis will increase self-reported drug effects compared with placebo cannabis.

c. Statistical plan including sample size justification and interim data analysis.

The proposed sample size of 40 study completers was estimated based on limited prior studies. One study found significant effects of transdermal nicotine and smoked cannabis on subjective drug effects with a sample size of N=20, suggesting that the proposed sample size for this study is adequate to detect interactive effects of nicotine and cannabis on subjective drug effects using a within subjects design (Penetar et al., 2005). Evaluation of pharmacodynamic drug effects using a within-subjects design reduces variability across dose administration sessions and significantly increases statistical power to detect differences on the proposed study outcomes. However, because we have a greater number of dose conditions, and because a primary outcome is amount of drug self-administration rather than self-reported drug effects, we expect the need for a greater sample size in this study.

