Initial data analyses will examine whether study completers differ from non-completers with regard to demographic or cannabis use variables. This will inform the generality of the results. We will also examine the data for missing values. When missing data are found in self-report measures we will impute scores by averaging the closest pre and post values when applicable, otherwise missing data will be treated as missing in analyses. Missing data is expected to be rare given that all assessments are conducted via computer and individual items cannot be skipped. However, it is possible that a time point could be missed due to severe drug effects. Data will be evaluated for normal distribution, skewness, kurtosis and appropriate modifications will be made for data that is not normally distributed. All hypothesis tests will be two-sided; α will be set at 0.05. Nicotine/tobacco self-administration data will be analyzed using 2-tailed t-tests comparing the consumption of each nicotine/tobacco product after active versus placebo cannabis pre-treatment. Additional planned comparisons will then be conducted to compare consumption of 3% versus 5% nicotine E-Cig use following active cannabis. Secondary analyses will be conducted using repeated-measures multiple regression to evaluate the effects of nicotine/tobacco product type (None, conventional cigarette, low dose E-Cig, and high dose E-cig) and time as within-subjects factors on subjective drug effect ratings, cardiovascular effects, craving, and cognitive performance effects during sessions in which active (10mg or 25mg THC) cannabis was administered. If sufficient variability in pre-study cannabis use exists in our final study sample, we will conduct exploratory analyses comparing less frequent vs heavy (e.g. daily) cannabis users on primary and secondary outcomes.

d. Early stopping rules.

The study will be stopped if new information is learned that indicates a serious risk to study participants.

7. Risks

a. Medical risks, listing all procedures, their major and minor risks and expected frequency.

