A potential risk of smoking cannabis is irritation of the throat/lungs. Acute administration of cannabis can produce tachycardia, intoxication, altered mood, impaired coordination, and cognitive deficits. Given that the dose of cannabis we will administer has demonstrated a favorable safety profile in our prior research, and given that the participants will be experienced with smoking cannabis, the risk of these negative cannabis-related effects or serious adverse events in the laboratory setting is minimal. There is no known risk of overdose or death related to cannabis /THC. In the unlikely event a participant experiences panic and/or paranoid reactions, research staff will engage the person in relaxation exercises and will suspend research procedures until the volunteer has regained comfort. These types of effects are typically of short duration. In the case of an extreme adverse reaction, we will call 911 for emergency treatment. Note that the BPRU is located directly across the street from the Johns Hopkins Bayview ER.

Participants may experience some mild discomfort when not using tobacco/nicotine in the present study. Symptoms of nicotine/tobacco withdrawal are time-limited and typically resolve without clinically significant problems. In case of an adverse event, a study physician is available via pager for assistance. Unpleasant side effects associated with using nicotine/tobacco may include sweating, lightheadedness, dizziness, nausea, and nervousness, though these effects are unlikely to be experienced by participants in the present study because they will be regular users of tobacco products and use will be self-titrated. Given that participants will be regular users of both tobacco cigarettes and e-cigarettes, they will also be familiar with the other more positive acute effects associated with using nicotine/tobacco (e.g., feelings of euphoria, and heightened arousal). We are not aware of any evidence that would suggest simultaneous administration of nicotine and cannabis will put participants at increased risk of experiencing adverse events than use of either drug alone, and, as highlighted in the background, these two substances are widely co-administered in the real-world (Schauer et al., 2015; Schauer et al., 2016).

Exposure to COVID-19 is a risk.

b. Steps taken to minimize the risks.

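### Missed self-report scores are filled with the average of their neighbours although severe drug effects may cause the miss, so a missed early drug-effect peak would be understated; the likely effect on results is small

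*Combined protocol and SAP*

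**What the plan says.** Section c of the Study Statistics gives one rule for missing self-report data: "we will impute scores by averaging the closest pre and post values when applicable". Where the rule does not apply, the value stays missing. The qualifier that ends the quoted sentence is not defined, and nothing excludes the first post-dose assessment.

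The paragraph continues: "Missing data is expected to be rare given that all assessments are conducted via computer". It then adds that "it is possible that a time point could be missed due to severe drug effects".

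Section 4a (Study Measures) schedules the Drug Effect Questionnaire "before (i.e., baseline), and approximately 5, 30, 60, 90, 120, 180, 240-and 360-min after cannabis exposure". The tobacco-effects scale and both craving questionnaires follow the same times. Section 4a (Baseline Assessments) places the baseline before drug administration.

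The planned secondary analysis is a repeated-measures regression on nicotine product type and time, "during sessions in which active (10mg or 25mg THC) cannabis was administered". Section b of the Study Statistics supplies the matching expectation: "We hypothesize that nicotine use will increase subjective drug effect ratings", relative to the session without nicotine. It also expects higher ratings after active than after placebo cannabis, but section c specifies no model for that comparison of ratings.

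**The concern.** The plan names a cause of missingness that is tied to the value being measured, then adopts a fill-in rule that ignores this. A rating missed because the drug effect was severe is probably high, yet the rule cannot return more than the higher neighbour. The entered number is then treated as observed, with no allowance for its being a guess and no sensitivity analysis.

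The first post-dose point is the worst case, since one of its two neighbours was recorded before any cannabis was smoked. For items such as drug effect, bad effect or paranoid, a severe early reaction would appear in the data as a moderate one. Time-point means in active sessions would be pulled down, and so would any active-versus-placebo comparison of ratings. Subjective effects are secondary variables in the Study Statistics, but they also belong to Objective 2, which section 2 labels primary.

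**Working it through.** The plan gives no figure for the rule's error or for a miss rate, so there is none to reproduce. The check applies the rule to the schedule.

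**Inputs from the documents.** Assessments at baseline, 5, 30, 60, 90, 120, 180, 240 and 360 minutes (section 4a); 40 completers (Study Statistics, section c); a mean peak drug-effect rating of 58 out of 100, the higher of the two quoted from prior studies (sections 4a and 6a).

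**Assumptions.** The documents give no time course, time of peak or baseline score. I assume a baseline B of 0 (20 as an alternative), exponential decline after the peak with half-life h from 20 minutes to no decline, and a missed score P of 58 to 90. The value 90 stands for a severe effect.

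**Missed 5-minute score, peak at 5 minutes.** Entry = (B + X30)/2, with X30 = P × 2^(−25/h). With B = 0 the entry is X30/2 whatever the true score was. Share lost = 1 − 2^(−25/h)/2. Shift of the 40-person mean at 5 minutes = P × share lost / 40.

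| h (min) | X30/P | Share lost | Shift, P = 58 | Shift, P = 90 |
|---|---|---|---|---|
| 20 | 0.420 | 79.0% | 1.15 | 1.78 |
| 30 | 0.561 | 71.9% | 1.04 | 1.62 |
| 45 | 0.680 | 66.0% | 0.96 | 1.48 |
| 75 | 0.794 | 60.3% | 0.87 | 1.36 |
| 120 | 0.866 | 56.7% | 0.82 | 1.28 |
| no decline | 1.000 | 50.0% | 0.73 | 1.13 |

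Spread over the eight post-dose times, one miss moves the average by 0.73/8 = 0.09 to 1.78/8 = 0.22 points.

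A higher baseline softens this. With B = 20 and P = 90, no decline gives (20 + 90)/2 = 55, a loss of 39%; h = 120 gives (20 + 77.9)/2 = 48.9, a loss of 46%; h = 45 gives (20 + 61.2)/2 = 40.6, a loss of 55%.

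**Missed 30-minute score, peak at 30 minutes.** If the 5-minute score is a fraction f of the peak, share lost = 1 − (f + 2^(−30/h))/2.
- f = 0.9, h = 120: 1 − (0.9 + 0.841)/2 = 13%.
- f = 0.4, h = 45: 1 − (0.4 + 0.630)/2 = 49% (48.5% before rounding).
- One case moves the 30-minute mean by 58 × 0.130/40 = 0.19 to 90 × 0.485/40 = 1.09 points.
- A 20-minute half-life would raise the loss to 37–62% for the same values of f.

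**Missed score on the declining limb.**
- At 60 minutes, entry/true = (2^(30/h) + 2^(−30/h))/2. The error is +10.9%, +3.9% and +1.5% at h = 45, 75 and 120.
- At 120 minutes, where the neighbours are 90 and 180, entry/true = (2^(30/h) + 2^(−60/h))/2. The error is −0.8%, −5.3% and −5.2%.
- With h = 20 the 60-minute entry is 59% too high, but the true score is by then only 15% of a 5-minute peak.

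**Product contrast in active sessions.** Equal numbers of equally biased entries in two conditions cancel in the difference. One extra missed 5-minute score in either condition shifts the contrast by 0.7–1.8 points, with the sign set by which condition has it. Assuming a between-session SD of 10 and residual SD of 8 or 15, the paired standard error is √(2 × (100 + 64)/40) = 2.86 or √(2 × (100 + 225)/40) = 4.03. The shift is then 0.73/4.03 = 0.2 to 1.78/2.86 = 0.6 of a standard error.

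**The case against.** The strongest reply is that the case will hardly ever occur. The plan expects misses to be rare, and the prior studies it cites report moderate mean effects without adverse events. After a panic or paranoid reaction staff "will suspend research procedures until the volunteer has regained comfort", and "These types of effects are typically of short duration"; an assessment might therefore be delayed and not lost, though the text does not say which. Section 4b allows a session to be repeated after data loss and gives missed cognitive time points as an example. The cognitive tasks share the questionnaire's schedule, so a time point lost to severe effects would usually qualify. All of this stands and is why the point is minor. It does not remove it: a repeat is discretionary, and it replaces a session with a severe reaction by a different one.

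The undefined qualifier could also be read to exclude the 5-minute point. No text does so, and both neighbours exist there.

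A reader might infer that the 5-minute score is the peak. That is an assumption; with a later peak the loss is smaller or differently placed.

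A reader might also infer that the rule works against the hypothesis that nicotine raises ratings. The documents do not support a direction. Access to nicotine begins only after cannabis exposure (section 4a), so products have had little time to differ at 5 minutes, and an extra miss in the no-nicotine session would move the contrast the other way.

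**Conclusion.** The point holds as a minor one. As written, the rule understates a drug-effect rating missed at an early peak and treats the entry as observed. The half-of-30-minutes result needs only a near-zero baseline, which is plausible for drug-effect items but should not be extended to craving scales. The loss of at least 50% also needs a 5-minute peak and a baseline of 0. The 13–49% range for a 30-minute peak assumes half-lives of 45–120 minutes and a 5-minute score at 90–40% of the peak. With those half-lives the error on the declining limb is small.

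Nothing here reaches the primary outcome variable, which is inhaled volume, or the vital signs or cognitive scores, since the rule covers self-report measures only. The planned product comparison is biased only if misses differ by product, in an unknown direction; for craving and liking items even the direction of the error in a single entry is unknown. The total effect depends on a miss rate that the documents do not give.

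**What to change.** In section c of the Study Statistics:

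- Delete the neighbour-average rule and leave missed self-report scores missing.
- Fit the planned repeated-measures analysis as a likelihood-based mixed model with product, time and their interaction, participant effects, and a within-session correlation structure chosen in advance that lets the variance differ by time point.
- Record the number of missed assessments and the reasons, and report them by condition.
- Because the model assumes missing at random, add one sensitivity analysis for drug-effect items only (for example drug effect, bad effect, paranoid). Set scores missed because of drug effects to a high value, such as the scale maximum as an upper bound. Do not apply it to craving or liking items.
- If a session is repeated after such a loss, also report the result using the original session.

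The cost is a few sentences, a reason field and one extra analysis. Intervals may be slightly wider. The model predicts from the participant's other scores and so shrinks toward typical values; it reduces the bias from severe-effect misses but does not remove it, hence the sensitivity analysis.

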Participant Discharge. Participants will be discharged after completing final assessments (approximately 5 hours post-drug exposure). At the end of each session, study staff will compare vital signs and cognitive/psychomotor performance (i.e., DSST, PASAT, and DRUID App scores; see *Baseline Assessments* above) with baseline data and engage in face-to-face conversation with the participant to ensure that they are fit to leave the unit. If the participant is able to cognitively engage with staff, vital signs are within normative range (HR < 100bpm, SYS BP < 150mmHg, DIA BP < 90mmHg), and scores on the cognitive tests are within 20% of baseline, the participant will be cleared to leave without further evaluation. If any of these parameters are not met, medical staff will assess the participant. If the participant continues to exhibit behavior indicative of impairment/intoxication, the participant will be asked to remain at the BPRU until the drug effect subsides and their performance on the cognitive test battery is within 20% of baseline. If vital signs are out of range, then medical staff will evaluate and make a determination with regards to whether it is safe for participant to be discharged or remain under observation. Participants will not be allowed to drive home; instructions will be provided at the screening session regarding the need to make alternative transportation arrangements. If a participant fails to arrange a ride, taxi transportation home will be coordinated by study staff and provided free of charge. This same protocol will be followed for cases in which a study participant has undergone drug administration but indicates the desire to be discharged from the study early. Based on our prior studies, we do not anticipate the proposed doses of cannabis (10 mg or 25 mg THC) will produce impairment that would prohibit participants from being discharged. That is, using similar participants (i.e., healthy individuals with intermittent cannabis-use patterns; (Spindle, 2018)), we have demonstrated that smoked cannabis with 10 mg THC produces discriminable drug effects (e.g., mean peak rating of 46, on 100-point VAS) which subside within 5 hrs of exposure and does not significantly impair cognitive or psychomotor functioning when compared with placebo. Likewise, in a separate study with daily/near daily cannabis users, 25 mg THC produced discriminable drug effects (e.g., mean peak rating of 58, on 100-point VAS) which subsided within 5 hrs of exposure and did not significantly impair cognitive or psychomotor functioning when compared with placebo. Nicotine/tobacco exposure does not produce functional impairment and any nicotine-induced changes in vital signs are expected to be short-lived and return to baseline before discharge (Spindle et al., 2018).

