Participants are not a "vulnerable population" as defined by human subjects protection guidelines; that is, they are not minors, pregnant women, under legal coercion or restriction, or mentally impaired. They are competent adults who provide their voluntary informed consent. Participants will be recruited via media advertisements that clearly state the nature and intent of the study. The consent process will inform the participant in detail of the procedures, time involvement, compensation, risk, and treatment options other than participation in our study. Volunteers will also be instructed that they may withdraw from participation at any time without losing any of the compensation that they have earned to that point.

We feel that the risk of serious adverse events related to cannabis/nicotine exposure in this study is minimal – participants are experienced users of tobacco cigarettes, e-cigarettes, and cannabis, and thus they will be familiar with any acute drug effects they may experience in this study. The doses of THC we are administering (10 mg or 25 mg THC) are on the low end of the ranges used in prior studies and has demonstrated a favorable safety profile (i.e., produced mostly mild subjective drug effects without eliciting adverse effects) among individuals with the cannabis use profile we will recruit in this study. The cannabis doses are expected to produce positive discriminable drug effects without causing impairment of cognitive functioning or adverse events. Given that these individuals regularly use nicotine, they are not expected to experience negative nicotine-related side effects (e.g., nausea). Participants will be able to halt self-administration of either study drug (cannabis or nicotine) if they experience adverse effects. Similarly, study staff may halt the drug administration procedure if untoward drug effects are observed. Such effects

Date: July 15, 2022

Principal Investigator: [name]

Application Number: IRB00220975

are not expected for either nicotine or cannabis at the doses under investigation.

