The PI will follow ICH regulations (detailed in *Clinical Safety Data Management, Definitions, and Standards for Expedited Reporting*) regarding reporting of adverse events and all study deviations to the IRB and study sponsor.

d. Legal risks such as the risks that would be associated with breach of confidentiality.

Participants' names will be recorded only on the screening, informed consent, and necessary medical and payment forms. Anonymous participant identification numbers will be used on all other forms and labeling of test results. All information gathered will be kept in locked research staff offices or file cabinets. All medical information obtained will be handled in accordance with HIPAA regulations. Only research staff will have access to participant records. The limits of confidentiality (e.g. suspected child abuse or neglect, or harm to self or others) will be discussed in detail with the participants during the informed consent process. To reduce the likelihood of patient records disclosure, a Certificate of Confidentiality has been obtained for this study.

e. Financial risks to the participants.

This study does not involve patients receiving treatment; therefore, the financial risks are minimal. Participants will be fairly compensated for their time and effort in complying with the study protocol.

Date: July 15, 2022

Principal Investigator: [name]

Application Number: IRB00220975

8. Benefits

- a. Description of the probable benefits for the participant and for society.

The primary benefit of the proposed research is in the knowledge gained regarding the interactive effects of cannabis and nicotine/tobacco. The knowledge can be used to advise the treatment for disordered use of either of these drugs and provide insights into the mechanisms underlying the high rates of co-use of tobacco and cannabis. Because we anticipate relatively minor risks to these cannabis and nicotine-experienced healthy study volunteers, we feel that the proposed research has a positive risk benefit ratio.

9. Payment and Remuneration

- a. Detail compensation for participants including possible total compensation, proposed bonus, and any proposed reductions or penalties for not completing the protocol.

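### Performance-task readings missed because of severe drug effects are left missing, and no rule says which session counts after a repeat, so impairment after active cannabis may be understated

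*Combined protocol and SAP*

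**What the plan says.** The document is the combined protocol and SAP.

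- **Missing-data rule (Study Statistics, c).** For questionnaires: "When missing data are found in self-report measures we will impute scores by averaging the closest pre and post values when applicable". For all other measures: "otherwise missing data will be treated as missing in analyses". DSST, PASAT and DRUID are tasks, not self-report, so the second rule applies to them.
- **Foreseen cause (same paragraph).** Missing data are expected to be rare because testing is computerised and items cannot be skipped. The plan then allows that "it is possible that a time point could be missed due to severe drug effects". It names no other cause, asks for no reason code and plans no sensitivity analysis.
- **Repeat sessions (section 4b).** A participant may be invited to repeat a session after data loss, and gaps in cognitive testing are one of the examples. No rule says which session enters the analysis.
- **Secondary model (Study Statistics, c).** It compares four product conditions (none, cigarette, 3% and 5% e-cigarette) over time, within active-cannabis sessions only. Study Statistics, b, hypothesises that nicotine use worsens cognition in these sessions relative to the no-nicotine session.
- **Safety events.** Section 7b says "study staff may halt the drug administration procedure if untoward drug effects are observed". Section 4a (Participant Discharge) says that if impairment continues, "the participant will be asked to remain at the BPRU until the drug effect subsides". Section 7c commits the investigator to ICH rules "regarding reporting of adverse events and all study deviations to the IRB and study sponsor". The statistical plan does not summarise any of these by condition.

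**The concern.** The plan foresees that a reading may be lost because the participant is badly affected, which is what the task is there to measure. Leaving that reading out removes a value likely to be worse than those kept. The repeat provision can have the same effect by another route: if the second attempt is milder and is the one analysed, the severe session disappears.

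At stake are Objective 4 (cognitive performance) and the hypothesis that nicotine after active cannabis worsens cognition. If one product condition leaves more participants unable to complete the tasks, the observed-data comparison can miss that, and no planned table would show it.

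**Working it through.** **Inputs from the documents.** There are 40 completers, four active-cannabis sessions each (40 × 4 = 160) and eight post-dose time points per session. The plan gives no missing-data rate, task effect or SD, so there is no figure of its own to reproduce. The rates and deficits below are assumptions.

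**1. Mean deficit at one time point.** Let a share *s* of active-session readings be missed because of drug effects. Assume a true change of −*d*% for those and −5% for the rest.

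True mean = (1 − *s*)(−5) + *s*(−*d*). Analysed mean = −5. Share of deficit lost = 1 − 5/|true mean|.

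| *s* | *d* | True mean (%) | Share lost |
|---|---|---|---|
| 1% | 20 | −5.15 | 3% |
| 1% | 30 | −5.25 | 5% |
| 2.5% | 20 | −5.375 | 7% |
| 2.5% | 30 | −5.625 | 11% |
| 5% | 20 | −5.75 | 13% |
| 10% | 30 | −7.50 | 33% |
| 15% | 30 | −8.75 | 43% |

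The same arithmetic covers a repeated session: if the repeat gives a typical −5% and replaces the severe session, the analysed mean is again −5%.

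**2. The same question in SD units.** If missed readings are 2 SD worse than those observed, the mean is understated by *s* × 2: 0.02, 0.05, 0.10 and 0.20 SD at 1%, 2.5%, 5% and 10% (1.6, 4, 8 and 16 of 160 sessions). If exactly the worst tail of a normal distribution is lost, the shift is 0.03, 0.06, 0.11 and 0.20 SD.

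**3. Product contrast.** With equal deficits otherwise, the true difference between two product conditions is −(*s*₁ − *s*₂)(*d* − 5), and the observed-data difference is 0.

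- Equal shares: the true difference is 0, so there is no bias.
- 2.5% against 1%, *d* = 30: 0.015 × 25 = 0.375 points, estimated as 0.
- 10% against 2%, *d* = 30: 0.08 × 25 = 2.0 points, estimated as 0.

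If misses were commoner in the no-nicotine session, the sign would reverse and the effect of nicotine on cognition would be overstated.

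**4. What a descriptive event table could show.** With 40 people, an event with a 5% risk per person appears at least once with probability 1 − 0.95⁴⁰ = 0.87. With zero events, the one-sided 95% upper limit is 1 − 0.05^(1/40) = 7.2%. The table could bring such events to light. It could not establish that risks are equal.

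**The case against.** The case for leaving the plan alone has real weight.

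- **Rarity.** Missing data are expected to be rare, and sections 4a and 6a report no adverse events and no significant cognitive impairment in prior studies of these doses. This stands as a limit on size. It does not fully answer the point, because computerised testing prevents skipped items, not time points that an impaired participant cannot complete, and the plan concedes these.
- **Repeat sessions.** A reader might infer that nothing in the plan recovers such readings. That is wrong, because section 4b allows a repeat for this reason. Without a rule on which session is analysed, though, it may recover the data or replace a severe session with a milder one.
- **Other measurements.** The participant still contributes the remaining time points, and the Drug Effect Questionnaire records bad effect and paranoia. This stands in part, although filling a missed questionnaire score from its neighbours can flatten a peak.
- **Vital signs.** A reader might extend the concern to heart rate and blood pressure. The documents do not support that: nothing says severe effects prevent these readings, which require no task performance, and section 7b provides medical and nursing supervision throughout.
- **Under-reporting.** A reader might conclude that cannabis harms are under-reported. Section 7c still requires adverse events to go to the IRB and sponsor, and performance and vital signs are named outcomes. The documents support only that impairment may be understated in the trial's results.
- **Product contrast.** Misses that are equally common and equally severe across products cancel. This stands; bias needs a difference, and the documents give no evidence of one.

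**Conclusion.** The concern holds in limited form. The rule for DSST, PASAT and DRUID discards readings for the one cause the plan foresees, and the repeat provision has no analysis rule. Impairment after active cannabis may therefore be understated. The planned product contrast may be biased in either direction, but only if drug-related misses differ by product.

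The size is unknown. It is about 3-11% of the mean deficit at an assumed 1-2.5% share and 13-43% at 5-15%, with assumed deficits of −20% to −30% against −5%. The documents' expectation of rarity favours the lower range, so the upper range should not be read as a forecast. These figures apply to one time point and shrink when averaged over times that were not missed. The lack of an event summary by condition is secondary: it is mostly missing detail, but it matters here because such a summary would show the cases that drop out of the task data.

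**What to change.** In Study Statistics, c:

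1. Record a reason for each missed time point, with drug effects as one category.
2. Beside the observed-data model, add a sensitivity analysis that gives DSST, PASAT and DRUID readings missed because of drug effects the worst observed rank at that time point. Define worst separately for each score, since a high DRUID score means impairment whereas a low number correct does on the other two tasks.
3. State that when a session is repeated because of drug effects, the original session's data and reason are kept in this sensitivity analysis.
4. Report descriptively, by the seven conditions and in all dosed participants: adverse events, halted dosing, time points missed because of drug effects, and discharge checks not met at the first attempt. Keep these as separate rows. A composite would mix unlike events.

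This is a cheap improvement: plan wording, a reason code, one table and one sensitivity analysis. It adds no visit or procedure and changes no dose, discharge or clinical rule. The downside is a little extra analysis work, and counts so small that they support description only.
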